Acute skeletal muscle wasting is a common consequence of critical illness that occurs in up to 65% of patients admitted to the ICU. Critical illness myopathy (CIM), defined as a deficit in muscle size and strength that develops as a result of an ICU admission, is associated with high rates of short- and long-term morbidity and mortality, including decreased quality of life (QoL) due to persistent functional mobility impairments and inability to perform simple activities of daily living. Muscle dysfunction in the critically ill population is driven by underlying changes in cellular and molecular mechanisms leading to a net catabolic state. Rapid reductions in skeletal mass and strength lead to an increased risk of poor patient outcomes, including physical disability and mortality. The diagnosis of CIM in patients with acute respiratory failure or traumatic injury significantly increases the risk of in-hospital and long-term mortality. Recent data suggests that patients lose, on average, 19-27% of rectus femoris muscle size in the first ten days of critical illness. Little is known, however, about the significance of these changes in a subset of critically ill patients with acute kidney injury (AKI) requiring renal replacement therapy (RRT), also known as dialysis. The gold standard for assessing CIM is measurement by muscle biopsy or the analysis of psoas muscle area on a single cross-sectional CT imaging at the level of the L3 vertebra. Musculoskeletal ultrasound (MKUS), a non-invasive alternative, has gained significant traction over the last decade for assessing muscle in patients with critical illness. Studies have demonstrated that MKUS has excellent inter-rater reliability and high clinical utility, and have suggested that MKUS has strong construct validity. Recent data suggests that MKUS can be reliably performed at the ICU bedside, and our preliminary data suggests that graduate students in a healthcare-related field can reliably be trained to assess muscle mass in the ICU using MKUS in as little as 8 hours of training. Changes in rectus femoris size and quality (echo intensity) measured by MKUS were strongly correlated to muscle biopsies in patients with critical illness. In addition, MKUS measures have been shown to have clinical relevance. In a study of 102 surgical ICU patients, muscle wasting determined by MKUS was associated with increased rates of mortality and skilled nursing facility discharge. Acute kidney injury (AKI) is a commonly encountered condition that complicates 22.7% of all inpatient hospital admissions. More than half of all ICU admissions develop AKI, and 13.5% of all ICU patients will require renal replacement therapy (AKI-RRT) during their ICU stay. AKI is associated with poor short- and long-term prognosis. Even Stage 1 AKI is associated with a 10-fold increase in hospital mortality, and AKI-RRT has an in-hospital mortality rate >50%, making AKI-RRT one of the deadliest patient conditions encountered in U.S. hospitals. Even after discharge, patients with AKI continue to have worse outcomes. A meta-analysis of two million patients evaluating outcomes at least a year after admission showed that in-hospital AKI increased the risk of death. Despite how commonly AKI is observed and despite poor long-term outcomes, the rate of outpatient follow-up in this cohort is low. Therefore, patients with AKI are a high-risk, but underserved, group of patients that warrant further study and intervention. AKI of any stage is known to alter tissue utilization of amino acids. Studies have demonstrated that amino acid levels are reduced in AKI, and multiple, non-essential amino acids become conditionally essential. In addition, AKI leads to a state of increased amino acid oxidation, but reduced amino acid transport into muscle. Use of RRT may further exacerbate the issue by removing significant quantities of amino acids from the plasma. Amino acids are small and easily filtered during RRT, so daily losses of amino acids in effluent can be immense at up to 18 grams daily. While cross-sectional analyses demonstrate high clearance levels of amino acids during RRT, there are currently no published longitudinal data regarding amino acid levels. Because skeletal muscle is the major deposit of protein molecules, with nearly 60% of total body protein in humans, we hypothesize that patients with AKI-RRT are at even higher risk of CIM than critically ill controls without AKI.

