
## Objectives

List your research objectives. Please include a summary of intended research objectives in the box below.

Aim 1: Determine the rate and degree muscle wasting in critically ill patients with AKI-RRT vs historic ICU controls without AKI during ICU stay. Hypothesis 1: Patients with AKI-RRT have faster decline in rectus femoris and tibialis anterior muscle size compared to controls .

Aim 2: Determine the trajectory of muscle recovery in patients following an episode of AKI-RRT compared to matched controls by measuring muscle mass, muscle strength and power, and functional status in patients at discharge and at 1 and 3 months thereafter. Hypothesis 2: Patients with AKI-RRT will have a slower trajectory of muscle recovery following ICU discharge compared to matched patients without AKI.

Aim 3: Use trend analysis to determine that changes in plasma amino acid levels on RRT correlate with lean muscle loss during AKI-RRT and predict lack of muscle recovery at 1 and 3 months. Hypothesis 3: Trends in amino acid levels during treatment with RRT will correlate with MKUS determinations of lean body mass in the short-term and will predict lack of muscle recovery at 1 and 3 months.

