This is a prospective, non-blinded, non-randomized study to assess the impact of CRRT on critical illness muscle wasting. As the study is observational and non-interventional in nature, there will be no placebo administered in the course of the study. Patients will be identified based on conversations with ICU and Nephrology consult teams (in addition to chart screening) to determine which patients are likely to receive RRT therapy due to AKI and critical illness. In the first aim, patients will undergo musculoskeletal ultrasound (MKUS) assessments within 24 hours of CRRT initiation, and again at 48 hours and 168 hours. In addition, blood will be drawn at these timepoints and stored for later analysis. In Aim 2, the trajectory of muscle mass recovery will be determined through visits at the time of hospital discharge (to be completed within the hospital), and then at 1 and 3 months thereafter, which will entail separate visits. At these sessions, patients with AKI-RRT and matched controls will undergo measurements of muscle mass, strength, and function at hospital discharge and at 1- and 3-months following discharge. Measurements will include MKUS to determine CSA and muscle echogenicity in the RF and TA muscles. We will evaluate muscle strength by measuring: 1) Medical Research Council sum score (MRC-ss), a measure of global peripheral muscle strength that is the current clinical standard for diagnosing ICU-AW34, 2) Maximal isometric knee extensor and dorsiflexion muscle strength measured as peak force production and rate of force development38, and 3) Maximal isometric grip strength 40. Muscle power will be measured by the repetitive 5x sit-to stand test a reliable and validate measure of lower-extremity power. Physical function and frailty will be measured using 1) the Short Performance Physical Battery (SPPB), 2) six-minute walk test (6MWT), and 3) Clinical Frailty Scale. SPPB is a performance-based composite test with a total of 12 points including components of balance, chair to stand test, and 4-meter habitual gait speed. The 6-MWT assesses the distance a subject can walk in six minutes providing a global marker of physical function and representation of cardiopulmonary endurance. We will summarize descriptive statistics at each timepoint including mean and standard deviation or median and interquartile range, as appropriate. Independent t-tests and Mann-Whitney U tests for non-parametric data will be used as appropriate to compare differences in the testing outcomes between cases and controls at each timepoint. Two-way repeated measures ANOVA will be performed to assess the within change in muscle metrics over time and between group comparisons to understand the trajectories of muscle recovery.

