- Muscle strength/function assessment is anticipated to take 30-60 minutes.

Long-term follow-up and how it occurs

- Patients will be seen at 1 and 3 months follow-ups in the outpatient setting. Visit times and dates will be arranged prior to discharge if possible, or via telephone after discharge.

Variables collected from the chart will include the following:

- Demographic data (Age, Gender, Race, BMI)
- SOFA or APACHE score at initiation
- Comorbidities (Charlson Score)
- Cause of AKI (Sepsis, post-surgical, etc.)
- Location of ICU (medical vs surgical)
- Laboratory data at baseline (BMP, CBC, lactate, albumin, INR)
- Daily laboratory data
- % Volume overload at initiation and daily
- CRRT variables (BFR, dose, therapy fluid flow rate, UF, filtration fraction).
- Reason for filter loss
- Time to death (censored for patient drop out or loss to follow up)
- In-hospital Mortality
- Time to renal recovery (censored for interfering events)
- Renal Recovery at hospital discharge

What Control subjects will be asked to do/what happens in the study (in sequential order):

- At hospital discharge, the patient will undergo a series of muscle strength and function tests including 1)Medical Research Council sum score (MRC-ss), a measure of global peripheral muscle strength that is the current clinical standard for diagnosing ICU-AW, 2) Maximal isometric knee extensor and dorsiflexion muscle strength measured as peak force production and rate of force development, and 3) Maximal isometric grip strength. Muscle power will be measured by the repetitive 5x sit-to stand test a reliable and validate measure of lower-extremity power. Physical function and frailty will be measured using 1) the Short Performance Physical Battery (SPPB), 2) six-minute walk test (6MWT), and 3) Clinical Frailty Scale. SPPB is a performance-based composite test with a total of 12 points including components of balance, chair to stand test, and 4-meter habitual gait speed.

The time period over which procedures will occur:

- Muscle strength/function and MKUS will be assessed at hospital discharge, and at 1 and 3 months thereafter.

The time commitment for the subject for individual visits/procedures

- The time commitment will be 10-20 minutes for ultrasound procedures as above, and muscle strength/function assessment is anticipated to take 30-60 minutes.

Long-term follow-up and how it occurs

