- Patients will be seen at 1 and 3 months follow-ups in the outpatient setting. Visit times and dates will be arranged prior to discharge if possible, or via telephone after discharge.

Variables collected from the chart will include the following:

- Demographic data (Age, Gender, Race, BMI)
- SOFA or APACHE score at ICU admission

Comorbidities (Charlson Score)

- Cause of respiratory failure (COPD, PNA, etc.)
- Location of ICU (medical vs surgical)
- Laboratory data at baseline (BMP, CBC, lactate, albumin, INR)
- Daily laboratory data

Patients lost to follow-up:

-We will attempt to contact patients prior to their appointment to remind them about the 1 and 3 month visits, and we will attempt telephone contact of patients lost to follow-up.

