- Laboratory data at baseline (BMP, CBC, lactate, albumin, INR)
- Daily laboratory data
- % Volume overload at initiation and daily
- CRRT variables (BFR, dose, therapy fluid flow rate, UF, filtration fraction).
- Reason for filter loss
- Time to death (censored for patient drop out or loss to follow up)
- In-hospital Mortality
- Time to renal recovery (censored for interfering events)
- Renal Recovery at hospital discharge

What Control subjects will be asked to do/what happens in the study (in sequential order)

- At hospital discharge, the patient will undergo a series of muscle strength and function tests including 1) Medical Research Council sum score (MRC-ss), a measure of global peripheral muscle strength that is the current clinical standard for diagnosing ICU-AW, 2) Maximal isometric knee extensor and dorsiflexion muscle strength measured as peak force production and rate of force development, and 3) Maximal isometric grip strength. Muscle power will be measured by the repetitive 5x sit-to stand test a reliable and validate measure of lower-extremity power. Physical function and frailty will be measured using 1) the Short Performance Physical Battery (SPPB), 2) six-minute walk test (6MWT), and 3) Clinical Frailty Scale. SPPB is a performance-based composite test with a total of 12 points including components of balance, chair to stand test, and 4-meter habitual gait speed.

Variables collected from the patient's chart for control subjects will include:

- Demographic data (Age, Gender, Race, BMI)
- SOFA or APACHE score at ICU admission
- Comorbidities (Charlson Score)
- Cause of respiratory failure (COPD, PNA, etc.)
- Location of ICU (medical vs surgical)
- Laboratory data at baseline (BMP, CBC, lactate, albumin, INR)
- Daily laboratory data

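### Aim 2's repeated-measures ANOVA, as usually fitted, leaves out of the trajectory test any patient who misses an outpatient visit; a mixed model using all visits would not, at little cost

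*Protocol*

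**What the plan says.** Hypothesis 2 (Objectives) is about a trajectory: "Patients with AKI-RRT will have a slower trajectory of muscle recovery following ICU discharge compared to matched patients without AKI". Study Design sets three measurement times for cases and controls: discharge, in hospital, then 1 and 3 months later at separate visits. Research Procedures places the two later visits in the outpatient setting.

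Study Design names two kinds of between-group analysis. At each visit: "Independent t-tests and Mann-Whitney U tests for non-parametric data will be used as appropriate to compare differences in the testing outcomes". For the course over time: "Two-way repeated measures ANOVA will be performed to assess the within change in muscle metrics over time and between group comparisons". The second is the only test of trajectory. The text does not say how a patient with one missing visit enters it.

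On attendance, Background remarks of patients with AKI that "the rate of outpatient follow-up in this cohort is low". Research Procedures plans visits arranged before discharge where possible, reminders, and for absentees: "we will attempt telephone contact of patients lost to follow-up".

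On death, the chart variables for cases include in-hospital mortality and "Time to death (censored for patient drop out or loss to follow up". The control list, introduced by "Variables collected from the patient's chart for control subjects will include" in Data Collection & Research Materials and repeated in Research Procedures, has no item for death.

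**The concern.** A trajectory hypothesis is answered by the group-by-visit term, so it matters who contributes to that term. Repeated-measures ANOVA fitted in the usual wide layout needs all three values from a patient. Someone measured at discharge and 3 months but absent at 1 month is lost to the test, although both ends of the recovery curve were observed. The per-visit tests keep that patient, so the loss concerns the trajectory test only.

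Numbers are small. Project Information caps the study at 60 subjects, and Background puts in-hospital mortality in AKI-RRT above 50%. If 30 of the 60 were cases and half were discharged alive (both assumptions), about 15 cases would start Aim 2. Discarding visits already measured is then hard to justify.

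A smaller, related point is that, without a death item for controls, a control who dies after discharge cannot be told apart from one who does not attend, whereas for cases the two are separated.

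**Working it through.** **Inputs.** From the protocol: three visits, the first in hospital and the other two outpatient; two groups; the named ANOVA. It gives no attendance rate, SD or between-visit correlation for Aim 2, so there is no figure to reproduce and the following are assumptions: attendance a = 0.9, 0.8 or 0.7 at each outpatient visit (10, 20 or 30% missed), discharge always measured, unit SD, equal correlation r = 0.7 between visits, and the same attendance in both groups.

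**Target.** The group difference in change from discharge to 3 months, contrast c = (-1, 0, 1). Variances below are per discharged patient in one group; the ratio is the same for the group contrast.

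**Complete cases.** V_cc = 2(1 - r)/p = 0.6/p, where p is the fraction seen at all three visits.

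**All available visits.** V_all = c' I^-1 c, where I is the sum over attendance patterns of (pattern fraction) x (inverse covariance of the visits seen). If the same patients miss both visits this reduces to V_all = (1 - r^2)/a + (1 - r)^2. At a = 0.7 that is 0.51/0.7 + 0.09 = 0.819, against V_cc = 0.6/0.7 = 0.857, so the SD ratio is sqrt(0.857/0.819) = 1.023.

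**Long-format ANOVA.** One row per visit with patient as a factor. Patients with two visits stay in; those with discharge only add nothing to the change contrast.

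| Pattern of misses | a | p | V_cc | V_all | SD ratio, complete cases / all visits | SD ratio, long format / all visits |
|---|---|---|---|---|---|---|
| Independent | 0.9 | 0.81 | 0.741 | 0.648 | 1.069 | 1.003 |
| Independent | 0.8 | 0.64 | 0.938 | 0.710 | 1.149 | 1.007 |
| Independent | 0.7 | 0.49 | 1.224 | 0.792 | 1.243 | 1.012 |
| Permanent drop-out | 0.9 | 0.81 | 0.741 | 0.709 | 1.022 | 1.009 |
| Permanent drop-out | 0.8 | 0.64 | 0.938 | 0.860 | 1.044 | 1.018 |
| Permanent drop-out | 0.7 | 0.49 | 1.224 | 1.078 | 1.066 | 1.025 |
| Same patients miss both | 0.9 | 0.90 | 0.667 | 0.657 | 1.008 | 1.008 |
| Same patients miss both | 0.8 | 0.80 | 0.750 | 0.728 | 1.015 | 1.015 |
| Same patients miss both | 0.7 | 0.70 | 0.857 | 0.819 | 1.023 | 1.023 |

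For permanent drop-out, month-1 attendance is a and month-3 attendance is a^2, so completers match the independent case.

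**Sensitivity to r.** Over r = 0.5 to 0.85 the complete-case ratios run 1.068-1.255, 1.017-1.086 and 1.004-1.040 for the three patterns. The long-format ratio never exceeds 1.045.

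**Small samples.** With the covariance estimated from 15 per group (simulation, r = 0.7), the complete-case SD is 7/16/26%, 2/4/3% and 1-2% larger for the three patterns. The likelihood model's 95% interval missed the true value 6-9% of the time with normal quantiles and 5-7% with a degrees-of-freedom correction, so the correction is needed.

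**In patients.** With 15 cases discharged and 30% independent misses, 0.49 x 15 = 7.35, so about 7 remain in the trajectory test.

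**Bias.** In simulation with a true contrast of -0.40 SD, case non-attendance twice that of controls and dependent on discharge strength, complete-case means ran from -0.405 to -0.473, a shift of at most 0.07 SD. In a harsher large-sample run, where only the RRT group's absence depended on outcome, a true -0.50 was estimated at -0.55 to -0.60. When absence was unrelated to outcome there was no bias.

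**The case against.** The strongest reply is that the protocol names a method, not a deletion rule. A reader might infer that the plan drops every patient who misses a visit. It does not say so: listwise deletion is the common fit, but a long-format ANOVA keeps two-visit patients and is almost as precise as the mixed model, and some software fits a mixed model under this name. This stands. The 7-24% belongs to the listwise fit, which the protocol neither states nor excludes.

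Second, how incomplete patients are handled is ordinary SAP content, and this is an application form that asks only for a summary and lists a separate protocol file. That is fair as regards missing detail. But the form does commit to a named test for Hypothesis 2, and a better and cheap one is available. That is a comment on a stated choice.

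Third, a reader might take the remark on low follow-up as a forecast for this study. It is general background on AKI, carries no percentage, and says nothing of controls or of scheduled, reminded study visits. The mortality figure above 50% is likewise general to AKI-RRT. Both show why missed visits and small numbers deserve thought; neither gives a rate, so the rates used here remain assumptions.

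Fourth, a reader might infer that the unpaired per-visit tests are wrong because controls are called matched. The documents do not say whether matching is individual or by frequency, so that is not shown. Nor is it hidden that Aim 2 concerns patients discharged alive, since its first measurement is at discharge. Both are at most things to write down.

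**Conclusion.** The point holds in limited form. The named ANOVA, in its usual listwise fit, excludes from the only trajectory test any patient who misses one of two outpatient visits, and the protocol leaves open how such patients enter. At 10-30% missed per visit and r = 0.7 the SD is inflated by 7-24% if patients skip one visit and return independently, by 2-7% if they drop out for good, and by 1-2% if the same patients miss both. The protocol does not indicate which pattern to expect. A long-format fit would reduce the loss to about 0.3-2.5%.

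A reader might go further and call Aim 2 biased. The documents do not support that. Bias appeared only when absence depended on strength or outcome, was small when the same rule held in both groups, and was largest when outcome-dependent absence was confined to the RRT group. The cost is mainly precision. The change is worth making because it is cheap and was no less precise under any pattern in the table; the present choice does not invalidate the aim.

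The uneven recording of death is a small separate gap, plain from the two chart lists. Telephone contact may reveal some control deaths, but no listed variable stores them.

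**What to change.** - Replace the repeated-measures ANOVA with a likelihood-based mixed model using all available visits, with group, visit and group-by-visit terms and a small-sample degrees-of-freedom correction. Take the group-by-visit contrast at 3 months as the trajectory test for the continuous muscle measures.
- Keep the rank-based per-visit comparisons for ordinal or bounded scores: the MRC sum score, the Clinical Frailty Scale and the SPPB ("SPPB is a performance-based composite test with a total of 12 points").
- Record death from discharge to 3 months for controls as for cases, and report the numbers alive and attending at each visit by group.

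The cost is a change of analysis wording and one more data item for controls, with no new visits or patients. The model rests on a missing-at-random assumption and takes slightly more analysis work. If losses turn out to be permanent, the gain may be only a few percent.

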
## Attachments

## Subject Recruitment Methods & Advertising

Describe how the study team will identify and recruit subjects. Please consider the following items and provide additional information as needed so that the IRB can follow each step of the recruitment process.

- How will the study team identify potential participants?
- Who will first contact the potential subjects, and how?
- Will you use advertisements? If so, how will you distribute those?
- How and where will the research team meet with potential participants?
- If applicable, describe proposed outreach programs for recruiting women, minorities, or disparate populations.
- How you will minimize undue influence in recruitment?
- Attach copies of all recruiting and advertising materials (emails, verbal scripts, flyers, posts, messages, etc.).

For additional information on recruiting and advertising:

- [IRB Application Instructions - Advertisements](#)
- [PI Guide to Identification and Recruitment of Human Subjects for Research](#)

Patients will be recruited in Intensive Care Units. Methods of identification will include the use of any information available to the researchers/their colleagues because this person is a patient, or the use of any information considered to be PHI, or review of patient/clinic records. We will ask the Nephrology consult team to alert us when patients are going to start RRT, and we will obtain information (name and room number) that will allow us to locate and identify the patient for purposes of consent. We will only store information in REDCap secure data storage, and will not disclose identifiers to individuals who are not part of the research team, or not already part of the patient's research team. We plan to remove identifiers from the REDCap database upon completion of the project. If a patient (or LAR) is approached to participate and chooses not to, we will at that time remove any existing data from the database regarding that patient.

N/A

Attachments

